## **7.2. Schedule of Visits and Assessments**

The schedules of visits and assessments are shown in [Table 1](#).

For a missed visit, the site should attempt to contact the subject to reschedule.

Premature discontinuation procedures are provided in [Section 6.3](#).

**Table 1: Schedule of Visits and Assessments**

	Screening	Treatment Period 						
		Day 1	Month 1	Month 2	Month 3 	Month 4	Month 5	Month 6 EOT/ET
		V1	V2	V3	V4	V5	V6	V7
Visit windows (days)		Day 1	22-36	37-64	65-92	93-120	121-148	149-183
4 week dosing target day		1	29	57	85	113	141	169
6 week dosing target day		1	May skip Visit 	43	85	May skip Visit 	127	169
Study Drug Administration		Injections are to be given monthly (6 total injections) or every 6 weeks (4 total injections) based on the dosing regimen selected; After Day 1, subsequent injections will occur 28 or 42 days following the previous injection						
Informed Consent	X							
Eligibility Criteria Review 	X	X						
Oral Aripiprazole Test Dose Administration 	X							
Drug Screen 	X							
12-Lead ECG	X							
Demographics and Medical History	X							
Reason for switching paliperidone/risperidone	X							
MINI (Modules I & J)	X							X
Height	X							
Pregnancy Testing 	X	X						

**Table 1: Schedule of Visits and Assessments (Continued)**

Visit windows (days)	Screening	Treatment Period 						
		Day 1	Month 1	Month 2	Month 3 	Month 4	Month 5	Month 6 EOT/ET
		V1	V2	V3	V4	V5	V6	V7
Visit windows (days)		Day 1	22-36	37-64	65-92	93-120	121-148	149-183
Physical Exam 	X	X						
Adverse Event Monitoring	X	X	X	X	X	X	X	X
Concomitant Medication Review	X	X	X	X	X	X	X	X
Vital Signs, Weight, Waist Circumference 	X	X	X	X	X	X	X	X
ESRS-A		X			X			X
Clinical Lab Tests 	X	X	X 	X 	X 			X
Modified MSQ	X 							X 
Modified UKU	X	X						X
CSFQ-14	X	X						X
Injection Site Evaluation 		X	X	X	X	X	X	X
C-SSRS 	X	X	X	X	X	X	X	X
TSR-6-Modified	X	X	X	X	X	X	X	X
CGI-S	X	X	X	X	X	X	X	X
BPRS	X	X	X	X	X	X	X	X
QLS	X				X			X
NSA-16	X				X			X
NY-AACENT	X							X

**Table 1: Schedule of Visits and Assessments (Continued)**

Visit windows (days)	Screening	Treatment Period 						
		Day 1	Month 1	Month 2	Month 3 	Month 4	Month 5	Month 6 EOT/ET
		V1	V2	V3	V4	V5	V6	V7
Visit windows (days)		Day 1	22-36	37-64	65-92	93-120	121-148	149-183
PSP	X				X			X
BIS	X							X
Burden Assessment Scale	X							X
CarerQOL-7D+VAS	X							X

EOT= end of treatment; ET= early termination; ECG= electrocardiogram; MINI = Mini International Neuropsychiatric Interview; ESRS-A=Abbreviated Extrapyramidal Symptom Rating Scale; MSQ= Medication Satisfaction Questionnaire; UKU= Udvælg for Kliniske Undersøgelser Side Effect Rating Scale; CSFQ-14=Changes in Sexual Functioning Questionnaire Short Form; C-SSRS= Columbia Suicide Severity Rating Scale; TSR-6= Sixth edition of the Treatment Services Review; CGI-S= Clinical Global Impressions-Severity; BPRS= Brief Psychiatric Rating Scale; QLS = Quality of Life Scale; NSA-16 = Negative Symptom Assessment-16; NY-AACENT= New York Assessment of Adverse Cognitive Effects of Neuropsychiatric Treatment; PSP= Personal and Social Performance scale; BIS= Birchwood Insight Scale; CarerQOL-7D+VAS= Caregiver Quality of Life – burden dimensions and visual analog scale

 For all visits other than Screening and Day 1, the visit will be anchored to the previous visit (based on dosing regimen schedule)

 In the event the Month 3 visit is missed or skipped, the additional assessments required at the Month 3 visit (ESRS-A, prolactin, QLS, NSA-16, PSP) should be conducted (via unscheduled assessment) at the subject's next visit

 Visits may be skipped for subjects on a 6 week dosing regimen

 Eligibility Review Form must be reviewed by **PPD** Clinical Surveillance Team (CST) prior to enrolling a subject on Day 1

 Only for prospective subjects who have never received aripiprazole. The oral aripiprazole test doses will consist of 5 mg/day for 2 consecutive days during the screening period. The first test dose should be administered at the clinic.

 Urine drug screen via dipstick at screening. The urine drug screen includes amphetamines, barbiturates, cocaine, methadone, opiates, and phencyclidine. Rescreening may be performed if positive results cannot be confirmed by a history of presumed active substance use or use of prescribed medications, which may account for the positive urine drug test results.

 Urine pregnancy testing will be completed for ALL women. At screening, pregnancy test should be completed prior to the administration of the first oral aripiprazole test dose, where applicable. On Day 1, testing will be performed before dosing.

 Full physical examination at screening; brief physical examination on Day 1; symptom directed physical exams may be performed as needed at the Investigator's discretion.

 Vital signs include blood pressure, heart rate, respiratory rate, and body temperature,

 Includes biochemistry (including prolactin), hematology, and urinalysis.

 Prolactin only will be measured at Month 1, Month 2 and Month 3.

Modified MSQ question #1 only at screening; the entire modified MSQ will be completed at Visit 8 (EOT)

The injection site and surrounding area will be evaluated following each injection and monitored so long as there are reactions to be monitored; if there are no observed reactions, continuing evaluation is not necessary

“Baseline” version used at screening; “since last visit” used at all subsequent visits

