## 1. SYNOPSIS

Name of Sponsor/Company: Alkermes, Inc.	
Name of Product: Aripiprazole lauroxil	
Name of Active Ingredient: Aripiprazole	
Title of study: Safety and Tolerability of Initiating Aripiprazole Lauroxil in Subjects with Schizophrenia who are Inadequately Treated with Paliperidone Palmitate or Risperidone Long Acting Injection	
Study Center Multicenter study (United States [US])	
Study Period: Estimated date of first subject's consent: Q4 2015 Estimated date of last subject's last visit: Q3 2017	Phase of Study: 4
Objectives:	
Primary: 

To evaluate the safety, tolerability, and efficacy of aripiprazole lauroxil in subjects with schizophrenia who are inadequately treated with paliperidone palmitate or risperidone long acting injection

	
Secondary: 

To evaluate quality of life, including daily and social functioning, after treatment with aripiprazole lauroxil

To characterize the caregiver and healthcare burden

	

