**Figure 1: Study Design (ALK9072-A401)**

Potential subjects will be evaluated for eligibility according to the inclusion and exclusion criteria at a screening visit and again on Day 1. The first dose of aripiprazole lauroxil will be administered on Day 1. Subjects will receive their first dose of aripiprazole lauroxil no earlier than one week and not later than six weeks following their previous injection of paliperidone palmitate or risperidone. The cross-tapering from risperidone or paliperidone to aripiprazole lauroxil is facilitated by the gradual disappearance of plasma risperidone/paliperidone while aripiprazole is concomitantly released from the initial IM aripiprazole lauroxil injection.

For subjects who have never taken aripiprazole, two test doses of oral aripiprazole 5 mg will be administered during the screening period. Only subjects who exhibit tolerability to oral aripiprazole (either following test doses or by past experience) are eligible to enroll in the study.

On Day 1, qualified subjects will be administered a single IM injection of aripiprazole lauroxil into the gluteal (441, 662 or 882 mg) or deltoid muscle (441 mg), according to the dosing instructions ([Section 8.1](#)). Following the first injection, subjects will return to the study site monthly or every 6 weeks (882 mg, gluteal IM only) for IM aripiprazole lauroxil administration and outpatient assessments. Additional outpatient assessments may be scheduled at the discretion of the investigator.

Efficacy will be evaluated based on Clinical Global Impressions-Severity (CGI-S) and Brief Psychiatric Rating Scale (BPRS) responses.

Safety and tolerability will be evaluated based on adverse events (AEs), injection site reactions (ISRs), clinical laboratory data, vital sign data, Columbia Suicide Severity Rating Scale (C-SSRS) responses, and Abbreviated Extrapyramidal Symptom Rating Scale (ESRS-A) scores. Potential changes in informant-rated cognition, insight, treatment satisfaction, quality of life, daily and social functioning, caregiver and healthcare burden, and psychosocial care needs following a transition to aripiprazole lauroxil will be examined. Total healthcare costs as measured by TSR-6-(Modified for Mental Health) survey will also be evaluated.

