### **7.3.9. Extrapyramidal Symptom Rating Scale – Abbreviated**

The ESRS-A is a questionnaire that assesses the severity and/or frequency of drug induced movement disorders (eg. Parkinsonism, dystonia, dyskinesia, and akathisia) ([Chouinard and Margolese 2005](#)). The investigator or designee will administer the ESRS-A scale at time points specified in [Table 1](#). A sample of the ESRS-A can be found in [Appendix B](#).

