## 8. TREATMENT OF SUBJECTS

### 8.1. Study Drug Dose and Administration

The initial dose of aripiprazole lauroxil will be selected according to the investigator's judgment and will be prepared and administered in accordance with the Directions for Use.

Depending on individual patient's needs, treatment with aripiprazole lauroxil can be initiated at a dose of 441 mg, 662 mg or 882 mg administered monthly, which corresponds to 300 mg, 450 mg and 600 mg of aripiprazole, respectively. Treatment may also be initiated with the 882 mg dose every 6 weeks.

Subjects will receive their first dose of aripiprazole lauroxil no earlier than one week and not later than 6 weeks following their previous dose of injectable risperidone or paliperidone. Due to safety concerns and the potential for rapid emergence of adverse events including akathisia, dystonia and EPS, oral aripiprazole dosing for 21 days after the initial dose of aripiprazole lauroxil is not recommended. Cross-tapering patients from long acting injectable risperidone or paliperidone palmitate to aripiprazole lauroxil is facilitated by the gradual disappearance of plasma risperidone/paliperidone while aripiprazole is concomitantly released from the initial IM aripiprazole lauroxil injection.

Administer aripiprazole lauroxil either in the deltoid muscle (441 mg dose only) or gluteal muscle (441 mg, 662 mg or 882 mg). See Table 3.

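### The ESRS-A is first repeated at Month 3 (target Day 85), so the first 9 to 13 weeks after initiation have no scheduled extrapyramidal rating

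*Protocol*

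**What the plan says.** The study title in the protocol synopsis is "Safety and Tolerability of Initiating Aripiprazole Lauroxil in Subjects with Schizophrenia who are Inadequately Treated" with paliperidone palmitate or risperidone long acting injection. Safety and tolerability are part of the primary objective (Protocol 5.1), and Protocol 13 lists the ESRS-A among the safety measures.

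The ESRS-A row of Table 1 (Protocol 7.2) has three marks: Day 1, Month 3 and Month 6 EOT/ET. Protocol 7.3.9 adds none: "The investigator or designee will administer the ESRS-A scale at time points specified in" Table 1. Footnote 2 says that if Month 3 is missed or skipped, "the additional assessments required at the Month 3 visit (ESRS-A, prolactin, QLS, NSA-16, PSP") move to the next visit as an unscheduled assessment.

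Other measures follow the early weeks more closely. CGI-S, BPRS, C-SSRS and adverse event monitoring are marked at every visit, and footnote 11 adds prolactin at Months 1, 2 and 3.

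Protocol 7.1 describes the switch as a "gradual disappearance of plasma risperidone/paliperidone while aripiprazole is concomitantly released from the initial IM aripiprazole lauroxil injection". Protocol 4 names akathisia among the most common adverse events in previous trials.

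On the analysis side, SAP 3.7.8 summarizes the ESRS-A subcategories and total. SAP 3.7.1 tabulates TEAEs by system organ class, preferred term, severity and relatedness, but not by time of onset. SAP 6.1 keeps unscheduled measurements out of the summary tables, except for the potentially clinically significant (PCS) analysis.

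**The concern.** The trial sets out to describe what happens when patients start this drug while the previous injection is wearing off. Akathisia, dystonia or parkinsonism that begins after the first injection and settles before Month 3 would leave no extrapyramidal scale record in a patient who stays in the study. The Month 3 rating is then taken in those who remained. Its objective akathisia item rests on what is seen at that examination, so it cannot recover signs that have gone.

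The risk lies in how the table will be read. An unchanged mean from Day 1 to Month 3 invites the conclusion that switching carried no extrapyramidal cost, although the early part of the switch was not rated.

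There is also an effect on efficacy. BPRS item 6 rates observed motor restlessness and tells the rater to ignore its presumed cause. Restlessness from early akathisia can therefore raise the BPRS total at Month 1 or 2 and look like symptom worsening, with no ESRS-A at the same visit to help tell them apart.

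**Working it through.** This is schedule arithmetic. The plan has no sample size calculation, and the point does not depend on one.

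**Inputs, all from Protocol Table 1**
- Monthly targets: "4 week dosing target day 1 29 57 85 113 141 169".
- Windows for Months 1 to 4: "22-36 37-64 65-92 93-120".
- Injection interval: 28 or 42 days.
- Six-week regimen: Month 1 and Month 4 are optional (footnote 3: "Visits may be skipped for subjects on a 6 week dosing regimen").

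**Reproducing the plan's own dates**
- Monthly: 1 + 28k gives Days 1, 29, 57, 85, 113, 141 and 169. Six of these fall before Day 169, matching the stated 6 injections.
- Six-weekly: 1 + 42k gives Days 1, 43, 85, 127 and 169. Four fall before Day 169, matching the stated 4.
- Month 3 is Day 85 on both: 1 + 3 × 28 = 1 + 2 × 42 = 85.

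**Time to the first post-baseline ESRS-A**
- At target: 85 − 1 = 84 days, or 12 weeks.
- Across the window: 65 − 1 = 64 days (9.1 weeks) to 92 − 1 = 91 days (13.0 weeks).
- Share of Day 1 to Day 169: 84 / (169 − 1) = 84 / 168 = 50%.
- Injections already given before Day 85: three on the monthly regimen (Days 1, 29, 57) and two on the six-week regimen (Days 1, 43).

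**If Month 3 is missed**
- Monthly: the make-up rating falls at Month 4, 113 − 1 = 112 days after the first dose.
- Six-weekly with Month 4 skipped: Month 5, 127 − 1 = 126 days.
- Footnote 2 makes this rating unscheduled, so SAP 6.1 leaves it out of the summaries. For a completer, the first summarized post-baseline ESRS-A could then be Month 6.

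**What else could record an early extrapyramidal event**

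| Source | When | Limit |
|---|---|---|
| Adverse event monitoring | Every attended visit | Not a scale; no onset-time table in SAP 3.7.1 |
| BPRS items 6 and 13 | Every attended visit | Non-specific; SAP 3.5.2 summarizes only the total |
| ESRS-A at an ET visit | On withdrawal | Early leavers only; shares a Table 1 column with Month 6 |
| Symptom-directed examination, extra visits | Investigator's discretion | Not scheduled |

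**With the ESRS-A added at Months 1 and 2**
- Monthly: first repeat at 29 − 1 = 28 days (window 21 to 35).
- Six-weekly with Month 1 skipped: 43 − 1 = 42 days (window 36 to 63).

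**The case against.** The strongest reply is that this is a preference about assessment frequency in a descriptive study of about 50 subjects. Baseline, midpoint and end is a common pattern, and the 50% figure follows from any such schedule. Adverse events are elicited at every visit with severity and causality, they head the list of safety measures, and neither document plans a claim that switching has no extrapyramidal cost. This stands as far as it goes: the plan does not contradict itself and no endpoint becomes unanalyzable. But none of these sources is a scored early movement rating, and the SAP does not use adverse event timing in its place.

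Four stronger readings are tempting, and the documents do not support them.

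- **That Month 3 falls after the overlap with the previous drug.** Neither document gives the overlap a length. Protocol 8.1 also describes aripiprazole levels building up over the first monthly doses, so Month 3 could lie within that period.
- **That Protocol 8.1 identifies rapid extrapyramidal onset as a known effect of the injection.** The phrase "Due to safety concerns and the potential for rapid emergence of adverse events including akathisia, dystonia and EPS" opens a sentence that advises against 21 days of oral aripiprazole after the first injection. It shows awareness of the risk when oral drug is added, and is only indirect support here.
- **That skipping Month 1 causes the gap.** No subject has an ESRS-A at Month 1. Skipping it removes a visit at which adverse events would be elicited, which is a separate and smaller matter.
- **That early symptoms leave no record at all.** They leave no extrapyramidal scale record in subjects who stay. The sources in the table above still give partial capture.

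**Conclusion.** The point holds as a gap in measurement. Between the first injection and Day 65 at the earliest, the schedule contains no movement-disorder rating, in a trial whose title is about initiation. The size is 84 days at target (64 to 91 across the window), covering three monthly or two six-weekly injections. The same visits already carry BPRS, CGI-S, C-SSRS and prolactin.

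The conclusion that an unchanged Month 3 ESRS-A cannot vouch for the early switch needs one assumption: that some extrapyramidal symptoms start and settle within that time. The documents give no rate or duration for this, so the number of subjects affected cannot be estimated. The conclusion does not need the overlap to be over by Month 3. If it lasted longer, the Month 3 rating would fall inside it, and the first 9 to 13 weeks would still be unrated.

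The Month 3 score has a second limit. Dose increases are allowed after the second injection, before the first repeat rating, so it may reflect later dose changes as well as initiation.

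**What to change.** 1. **Protocol Table 1:** mark the ESRS-A at Month 1 (V2) and Month 2 (V3), to be done whenever those visits are attended. Six-week subjects who skip V2 are then first rated at V3. No visit becomes compulsory.
2. **SAP 3.7.1:** tabulate akathisia, dystonia, parkinsonism and dyskinesia TEAEs by onset: first to second injection, second injection to Month 3, and after Month 3. At target dates these intervals last 28, 56 and 84 days on the monthly regimen and 42, 42 and 84 on the six-week regimen, so show the number of subjects at risk in each.
3. **SAP 3.7.8:** add the worst post-baseline ESRS-A score beside the visit scores, counting ET and make-up assessments, with a stated exception to SAP 6.1. A maximum tends to rise with the number of ratings, so report how many each subject had.

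The cost is one further administration of a scale already in use at each of up to two existing visits, plus two tables. The scale includes a physical examination of rigidity, gait and posture, and the documents do not say how long it takes. If the protocol can no longer be amended, items 2 and 3 need no new data collection. They would show when reported events began, but would not supply the missing early ratings.

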### **7.3. Study Procedures Descriptions**

Details of the study procedures are described below. The overall schedules of assessments are provided in [Table 1](#).

#### **7.3.1. Informed Consent**

The nature of the study and its risks and benefits will be explained to the subject and caregiver by the principal investigator or designated study personnel as outlined in [Section 17.3](#).

Prior to the administration of any study-specific procedures, authorized study personnel will obtain written informed consent from each potential subject and caregiver.

#### **7.3.2. Eligibility Review**

An eligibility review will be conducted by the investigator at the visits specified in [Table 1](#) using the subject inclusion criteria in [Section 6.1](#) and exclusion criteria in [Section 6.2](#).

#### **7.3.3. Demographics and Medical History**

Subject's demographic data and medical history will be reviewed and documented at the time point(s) specified in [Table 1](#).

#### **7.3.4. Concomitant Medication Review**

At the time point(s) specified in [Table 1](#), prospective subjects will be asked about the medications they have taken since the last visit and are currently taking, including prescription and nonprescription medications, vitamins, and supplements.

The investigator will record the following data on all medications used by the subject: name, dose, regimen, route of administration, start and stop dates, and the indication for use.

#### **7.3.5. Vital Signs, Weight, and Waist Circumference**

Vital signs (blood pressure, heart rate, respiratory rate, and body temperature), waist circumference, and weight will be assessed at the time point(s) specified in [Table 1](#). Blood pressure, heart rate, and respiratory rate will be measured after the subject has been resting in a seated or supine position for at least 5 minutes.

#### **7.3.6. Physical Examination**

A full physical examination will be performed at screening and a brief physical exam performed on Day 1. Symptom-directed physical exams may be performed as needed at the Investigator's discretion.

#### **7.3.7. 12-Lead Electrocardiogram**

A 12-lead electrocardiogram (ECG) will be conducted at screening only.

### **7.3.8. Columbia Suicide Severity Rating Scale**

The PI or designee will administer the C-SSRS ([Appendix A](#)) according to the schedule in [Table 1](#). At screening, the “Baseline” version will be administered ([Posner, Brent et al. 2009](#)), and at all other visits, the “Since Last Visit” version will be administered ([Posner, Brent et al. 2009](#)). For “Since Last Visit” versions, subjects should be asked to report on ideation and behavior since the last scheduled C-SSRS assessment. The C-SSRS should be administered by a clinician trained to assess and manage suicidal ideation and behavior.

### **7.3.9. Extrapyramidal Symptom Rating Scale – Abbreviated**

The ESRS-A is a questionnaire that assesses the severity and/or frequency of drug induced movement disorders (eg. Parkinsonism, dystonia, dyskinesia, and akathisia) ([Chouinard and Margolese 2005](#)). The investigator or designee will administer the ESRS-A scale at time points specified in [Table 1](#). A sample of the ESRS-A can be found in [Appendix B](#).

## **7.3.10. Laboratory Assessments**

### **7.3.10.1. Drug Testing**

Subjects will complete a urine drug test for illicit amphetamines, barbiturates, cocaine, methadone, opiates, phencyclidine, at screening. A positive drug test will exclude the subject from the study. Repeat testing may be performed if positive results cannot be confirmed by a history of presumed active substance use or use of prescribed medications which account for the positive urine drug test results.

### **7.3.10.2. Hematology, Biochemistry, and Urinalysis**

Blood and urine samples will be collected at the time points specified in [Table 1](#) for specific hematology, biochemistry, and urinalysis assessments that are listed in [Table 2](#). Samples will be analyzed by a central laboratory. Laboratory assessments may be repeated at the investigator’s discretion.

**Table 2: Clinical Laboratory Assessments**

Hematology	Biochemistry	Urinalysis

 
• Hematocrit
 
• Hemoglobin
 
• Platelets
 
• Red blood cell count
 
• Total and differential (absolute) white blood cell count
 
	
 
• Albumin
 
• Creatine phosphokinase(CPK)
 
• Glucose
 
• Lactic dehydrogenase (LDH)
 
• Potassium
 
• Sodium
 
• Total protein
 
• Alanine aminotransferase(ALT)
 
• Alkaline phosphatase(ALK-P)
 
• Aspartate aminotransferase(AST)
 
• Gamma-glutamyl transferase (GGT)
 
• Total bilirubin
 
• Prolactin
 
• Blood urea nitrogen
 
• Creatinine
 
• HbA1c
 
• Total cholesterol
 
• LDL
 
• HDL
 
• Triglycerides
 
• TSH, at screening only
 
	
 
• Bilirubin
 
• Color and appearance
 
• Glucose
 
• Nitrite
 
• Occult blood
 
• pH
 
• Protein
 
• Specific gravity
 
• Urobilinogen
 

